7.1 Study completion and post-study treatment

Each subject will be required to complete the study in its entirety and thereafter no further study treatment will be made available to them.

Study completion is defined as when the last subject completes their Study Completion visit, and any repeat assessments associated with this visit have been documented and followed-up appropriately by the investigator, or in the event of an early study termination decision, the date of that decision.

All subjects should have a safety follow-up call conducted 30 days after last visit. The information collected is kept as source documentation. All SAEs reported during this period must be reported as described in [Section 9.2](#) and the Site Operations Manual. Documentation of attempts to contact the subject should be recorded in the source documentation.

7.2 Discontinuation of study treatment

Discontinuation of study treatment for a subject occurs when study treatment is stopped earlier than the protocol planned duration. Discontinuation of study treatment can be decided by either the subject or the investigator.

Study treatment must be discontinued and the subject withdrawn from the trial under the following circumstances:

- Any severe or serious adverse event considered at least possibly related to the study medications.
- Any other protocol deviation that results in a significant risk to the subject's safety

- Subject decision - subjects may choose to discontinue study treatment or withdraw informed consent for any reason at any time.
- The investigator believes that continuation would negatively impact the safety of the subject or the risk/benefit ratio of trial participation.
- Pregnancy (see [Section 8.6](#)) and [Section 9.6](#) (Pregnancy reporting)
- Use of prohibited treatment as per recommendations in [Section 5.2](#)
- For liver events, refer to [Section 15-Appendix 1](#): Liver Event Definitions and Follow-up Requirements).
- Patients who have a decline in PEF from the reference PEF (taken at screening) of $\geq 30\%$ for 5 of 6 consecutive scheduled PEF readings (includes readings taken at morning and evening) at any point during the study ([Section 4.2](#)).
- ≥ 3 consecutive days in any one treatment period in which ≥ 12 inhalations/day of SABA rescue medication were used
- Emergency department therapy resulting in the use of oral, parenteral, or non-study related inhaled corticosteroids therapy related to the treatment of worsened asthma.
- Use of prohibited treatment as per [Section 5.2](#) (Prohibited treatment).

Emergence of the following adverse events:

- Paradoxical bronchospasm as evidenced either by a significant increase in wheeze and dyspnea shortly after the administration of study drug or a fall in FEV₁ of $>20\%$ within 30 minutes of administration of study drug
- Reflex bronchoconstriction or other severe intolerance reaction to study drug inhalation
- If the absolute QTcF is >500 msec or an increase from pre-dose Treatment period 1 of >60 msec on two adequate ECGs at least a minute apart, second (if Mobitz Type 2) or third degree AV block, atrial or ventricular arrhythmias (as judged clinically significant by the investigator).
- Clinical asthma worsening which required additional asthma treatment other than study medication or study-defined rescue medication in any one treatment period.

If a liver event occurs, follow guidelines outlined in [Appendix 1](#) regarding discontinuation of study treatment.

Any of the following laboratory abnormalities:

- Random (non-fasting) plasma glucose greater than 15 mmol/L
- Serum potassium below the lower limit of the laboratory reference range if confirmed by a repeat test to exclude laboratory error
- Urine cotinine $>$ than the laboratory's lowest level of quantification (LoQ of 500 ng/mL or lower) after randomization (a positive test at screening would preclude inclusion into the study)

Discontinuation of study treatment and subject withdrawal will be at the discretion of the investigator, under the following circumstances:

- Clinically significant abnormal laboratory value(s) (as judged clinically significant by the investigator).
- The investigator deems discontinuation is necessary for the safety of the patient.

The appropriate personnel from the site and Novartis will assess whether study treatment should be discontinued for any subject whose treatment code has been broken inadvertently for any reason.

If discontinuation of study treatment occurs, investigator must determine the primary reason for the subject's premature discontinuation of study treatment and record this information on the Dosage Administration eCRF.

Subjects who discontinue study treatment or who decide they do not wish to participate in the study further should not be considered withdrawn from the study unless they withdraw their consent (see [Section 7.3](#)). Where possible, they should return for the assessments conducted on Day 15/End of Study Visit. If they fail to return for these assessments for unknown reasons, every effort (e.g. telephone, e-mail, letter) should be made to contact the subject/pre-designated contact as specified in [Section 7.4](#). (Lost to follow-up). This contact should preferably be done according to the study visit schedule.

After study treatment discontinuation, at a minimum, in abbreviated visits, the following data should be collected at clinic visits or via telephone/email contact until the subject's end of study visit:

- new /change in concomitant treatments
- adverse events/serious adverse events

The investigator must also contact the IRT to register the subject's discontinuation from study treatment.

Subjects who are prematurely withdrawn from the study for reasons other than safety may be replaced on a case by case basis.

7.3 Withdrawal of informed consent

Subjects may voluntarily withdraw consent to participate in the study for any reason at any time.

Withdrawal of consent from the study is defined as when a subject:

- Does not want to participate in the study anymore and
- Does not want any further visits or assessments and
- Does not want any further study related contacts and
- Does not allow analysis of already obtained biologic material.

In this situation, the investigator must make every effort (e.g. telephone, e-mail, letter) to determine the primary reason for the subject's decision to withdraw his/her consent and record this information.

Study treatment must be discontinued and no further assessments conducted, and the data that would have been collected at subsequent visits will be considered missing.

Further attempts to contact the subject are not allowed unless safety findings require communicating or follow-up.

7.4 Lost to follow-up

For subjects whose status is unclear because they fail to appear for study visits without stating an intention to discontinue or withdraw, the investigator should show "due diligence" by documenting in the source documents steps taken to contact the subject, e.g. dates of telephone calls, registered letters, etc. A subject should not be formally considered lost to follow-up until his/her scheduled end of study visit would have occurred.

7.5 Study stopping rules

The study will be halted with no further recruitment and dosing suspended for all study participants pending a safety review if two or more study-drug related SAEs are reported or if the aggregate of severity, frequency, and/or drug relatedness of AEs, in the opinion of the investigator or Novartis, merit halting the study. Further dosing may only commence if deemed safe after a full safety review by the Novartis Translational Medical Expert (TME) and investigator.

7.6 Early study termination by the sponsor

The study can be terminated by Novartis at any time for any reason. This may include reasons related to the benefit/ risk assessment of participating in the study, practical reasons (including slow enrollment), or for regulatory or medical reasons. Should this be necessary, subjects must be seen as soon as possible and treated as a prematurely withdrawn subject. The investigator may be informed of additional procedures to be followed in order to ensure that adequate consideration is given to the protection of the subject's interests. The investigator will be responsible for informing IRBs/IECs of the early termination of the trial.

8 Procedures and assessments

8.1 Assessment schedule

Table 8-1 Assessment Schedule

Epoch	Screening ²	Treatment period 1/ Treatment period 2/ Treatment period 3							Early discontinuation or Epoch completion ²⁰
Visit name	Screening	Treatment period 1/ Treatment period 2/ Treatment period 3							
Visit Numbers ¹									
Period 1		101					102	103	
Period 2	1	201					202	203	Washout ³
Period 3		301					302	303	
Study Day(s)	-15 to -1	1			2 to 13		14	15	15 to 25
		26			27 to 38		39	40	40 to 50
		51			52 to 63		64	65 ²²	None required
Time	-	-1h ⁵	0h	30min	1h	-	-1h ⁶	0h	24h
Physical examination	X	X							X
Hepatitis and HIV Screen	S								

Corporate Confidential Information

Alcohol Test, Drug Screen, and Cotinine Test	S								
Smoking history	X								
Pregnancy test ⁹	X ¹⁰	X ¹¹				X ¹¹			X ¹¹
Study drug administration			X ¹²			X ¹⁴		X ¹³	
Device training	S	X				X			
Reversibility	X ¹⁵								
Body height	X								
Body weight	X	X						X	X
Body temperature	X	X				X			X

Epoch	Screening ²	Treatment period 1/ Treatment period 2/ Treatment period 3								Early discontinuation or Epoch completion ²⁰			
Visit name	Screening	Treatment period 1/ Treatment period 2/ Treatment period 3											
Visit Numbers ¹		101		At home dosing	102		103	Washout ³	199 299 399				
Period 1	1	101			102		103						
Period 2		201			202		203						
Period 3		301			302		303						
Study Day(s)	-15 to -1	1		2 to 13	14		15	15 to 25	26 ^{3,4}				
		26		27 to 38	39		40	40 to 50	51 ^{3,4}				
		51		52 to 63	64		65 ²²	None required	65 ^{3,4}				
Time	-	-1h ⁵	0h	30min	1h	-	-1h ⁶	0h	30min	1h	24h	-	-
Blood pressure	X ¹⁶	X ¹⁶		X	X		X		X	X		X	
Pulse rate	X	X		X	X		X		X	X		X	
ECG evaluation	X	X		X	X		X		X	X		X	
Hematology	X									X ¹⁷		X	
Blood chemistry	X									X ¹⁷		X	
Urinalysis	X									X		X	
Serum potassium ¹⁸		See table below										X	
Glucose ¹⁸		See table below										X	
PK blood collection		See table below										X	
Spirometry		See table below										X	
Peak expiratory flow		X including home dosing days										X	
Patient ediary		X including home dosing days										X	
Adverse events		X											

¹ Visit structure given for internal programming purpose only

² After informed consent, screening procedures may be performed over more than 1 day/visit as long as it is completed during the defined screening epoch.

³ A washout (minimum of 7 days and maximum of 14 days from last dose on Day 14) must occur after completion of Treatment period 1 prior to beginning Treatment period 2 and after completion of Treatment period 2 prior to beginning Treatment period 3. There is no washout after Day 15 of Treatment period 3. A + 2 days washout window is allowed for each treatment. Study days are based on a 10 days washout period, Visit days may be adapted as per the actual washout period; 7-14 days allowed per protocol.

⁴ Assessments to be performed if subject terminates early or at V399 Study completion.

⁵ Pre-dose assessments on Day 1 may be completed any time on Day 1 prior to first dose. For Treatment period 1 only: Pre-dose, Day 1 assessments (with the exception of blood pressure, pulse, spirometry, PEF, diary entry, and device training) do not need to be repeated if screening assessments were completed within 7 days of Day 1 in Treatment period 1. All Day 1, pre-dose assessments must be completed for Treatment period 2 and 3.

⁶ Pre-dose assessments with the exception of spirometry may be completed any time on Day 14 prior to dosing

⁷

Corporate Confidential Information

⁹ Pregnancy assessments may be performed at a greater frequency if required by local regulations.

¹⁰ Serum pregnancy test

¹¹ Urine pregnancy test.

¹² For Treatment periods 2 and 3, dosing on site on Day 1 should be between 06:00am and 10:00am and +/-1h of the time on dosing on Day 1 of Treatment period 1.

¹³ For Treatment periods 1, 2 and 3 dosing on site on Day 14 should be between 06:00am and 10:00am and +/-1h of the time of dosing on Day 1 of the current Treatment Period.

¹⁴ At home study drug administration should be between 06:00am and 10:00am and +/-1h of the time on dosing on Day 1 of Treatment period 1.

¹⁵ Can be repeated once during screening if necessary

¹⁶ Both standing and supine/sitting blood pressure measurements are required at screening and at pre-dose Treatment period 1 only. Only sitting or supine blood pressure measurements are required for other visits. Subjects' positions during blood pressure collections should remain consistent between visits (sitting or supine throughout the study).

¹⁷ This assessment is completed on Day 65 of Treatment period 3 only

¹⁸ If value is outside the acceptable reference range, this assessment may be retested

¹⁹ Subject status information will be collected at the end of each epoch (screening, after each treatment period and at early discontinuation or study completion), in the Summary eCRF page.

²⁰ Subjects will complete these assessments when a subject early terminates or after the subject has completed Treatment periods 1, 2, and 3. These assessments are completed one time only.

²¹ SAE monitoring is to be conducted from informed consent signature to 30 days after the last IP administration.

²² For Treatment period 3 only, assessments listed in Epoch completion will be completed in addition to assessments listed for Day 65. For assessments that are listed in both Day 65 and in Epoch completion, the assessment is to be completed once.

Details for highly repetitive assessments

Epoch	Periods 1/2/3 Visit numbers	Study Day(s)	Time	Subjects domiciled	Pharmacogenetic	Hematology Biochemistry	Serum potassium ¹	Glucose ¹	PK blood collection	Spirometry
Screening ²	1	-15 to -1				X				X
	101	1	-1h ⁴		X ⁵		X	X		X
	201	26	30min				X	X		
	301	51	1h				X	X		
	Dosing at home	2 to 13 27 to 38 52 to 63								
Treatment period 1/2/3 ³	102 ⁶ 202 ⁶ 302 ⁶	14 39 64	-1h	X			X	X		
			-45min	X						X
			-15min	X					X	X
			0h	X						
			5min	X					X	X
			10min	X					X	
			15min	X					X	X
			30min	X			X	X	X	X
			1h	X			X	X	X	X
			2h	X					X	X
			4h	X					X	X
			8h	X					X	X
			12h	X					X	X
	103 ⁷ 203 ⁷ 303 ⁷	15 40 65	23h15	X						X
			23h45	X						X
			24h00	X		X			X	

¹ If value is outside the acceptable reference range, this assessment may be retested

² After informed consent, screening procedures may be performed over more than 1 day/visit as long as it is completed during the defined screening epoch.

³ A washout (minimum of 7 days and maximum of 14 days from last dose on Day 14) must occur after completion of Treatment period 1 prior to beginning Treatment period 2 and after completion of Treatment period 2 prior to beginning Treatment period 3. There is no washout period after Day 65 of Treatment period 3. A + 2 days washout window is allowed for each treatment. Study days are based on a 10 days washout period, Visit days may be adapted as per the actual washout period; 7-14 days allowed per protocol.

⁴ Pre-dose assessments on Day 1 may be completed any time on Day 1 prior to first dose.

For Treatment period 1 only: Pre-dose, Day 1 assessments (with the exception of blood pressure, pulse, spirometry, PEF, diary entry, and device training) do not need to be repeated if screening assessments were completed within 7 days of Day 1 in Treatment period 1. All Day 1, pre-dose assessments must be completed for Treatment period 2 and 3.

⁵ Collected on Day 1 of Treatment period 1 only

⁶ Pre-dose assessments with the exception of spirometry may be completed any time on Day 14 prior to dosing

⁷ Early discontinuation or Epoch completion assessments should be completed after completion of each treatment period or at any time a subject early terminates from the study (does not complete Treatment period 1, 2, or 3 per protocol). Day 65 of Treatment period 3 will also be the end of study visit. Subjects should be discharged from site after completing Day 65/Epoch completion visit.

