2.2 Secondary objective(s)

Secondary objective(s)	Endpoints related to secondary objective(s)

To assess the steady state pharmacokinetics of indacaterol after 14 days of treatment of orally inhaled indacaterol salts (maleate and acetate) in subjects with asthma.	
AUC_{0-24h,ss} and C_{max,ss}, T_{max,ss}, C_{min,ss}, C_{a,v,ss} and F_{rel}

To assess the bronchodilator effect of orally inhaled indacaterol salts (maleate and acetate) in subjects with asthma compared to placebo as measured by:
Time to peak FEV₁ on Day 14FEV₁, FEV₁ (% predicted), FVC, FVC (% predicted), FEV₁/FVC, and FEF_{25-75%} at each post-dose time point after 14 days of treatmentStandardized FEV₁ AUC from pre-dose to 4 h post-dose on Day 14 of treatment	
FEV₁, FVC, and FEF_{25-75%} after 14 days of each treatment period

To assess the bronchodilator effect of indacaterol acetate, indacaterol maleate, and placebo by comparing the pre-medication (morning (pre-dose) and evening) peak expiratory flow (PEF) rate collected between days 8 and 14 of each treatment.	
Peak expiratory flow rate collected daily between days 8 and 14 during all three treatment periods (indacaterol acetate, indacaterol maleate, and placebo)

To assess rescue medication usage for indacaterol salts (maleate and acetate) in comparison to placebo.	
Usage of rescue medications as reported by subjects via diary during each treatment arm

[figure not shown]
Secondary objective(s)	Endpoints related to secondary objective(s)

• To assess the safety and tolerability of indacaterol salts (maleate and acetate) in comparison to placebo of 14 days of treatment in each treatment period.	
• Safety assessments during each treatment period including:
• Adverse Events and Serious Adverse Events• Vital signs• Hematology• Blood Chemistry• Urinalysis• ECG evaluation

Corporate Confidential Information

3 Investigational plan

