Subjects who meet all of the eligibility criteria will be randomized to one of six treatment sequences as described in [Figure 3-1](#). They will receive their first dose on the morning of Day 1. Subjects will be dosed between 06:00 a.m. and 10:00 a.m. under the guidance and supervision of the investigator or designee after an additional training for correct use of the Concept1 inhalation device. Dosing of investigational product and background ICS medication should occur at approximately the same time of the day throughout the study. For details of administration of investigational product please refer to [Section 6.5](#). PEF measurements (if not already performed at home on the morning of Day 1 or Day 14) should be taken prior to pre-dose spirometry and safety assessments

For further details, refer to the [Assessment schedule](#).

On Day 1, subjects will leave the clinic after the completion of the required assessments and will dose at home once daily in the morning on Days 2 to 13. During days 2 -13, subjects will record drug administration, PEF measurements, mouth rinsing, and rescue medication use in their diary. Subjects will be domiciled at the clinic on the morning of Day 14, for drug administration and Day 14 visit assessments. For details, refer to the [Assessment schedule](#). Subjects will be discharged on Day 15 following the final PK and safety blood sample draw and completion of Day 15 assessments.

A washout period of 7 - 14 days will separate each treatment period. Apart from the pre-dose spirometry and safety assessments on Day 1 which will only be done before Treatment period 1, the assessments for Treatment Periods 2 and 3 will be identical to Treatment period 1 (refer to the [Assessment schedule](#) for Treatment periods 2 and 3 assessments).

Epoch Completion assessments must be conducted for subjects who complete all three treatment periods or at any time a subject early terminates from the trial. The last visit (Day 65) of Treatment period 3 will also be the end of study visit. For assessments that are listed in both Day 65 and in Epoch completion, the assessment is to be completed once. Subjects should be discharged from the site after the completion of Day 15 assessments for all 3 periods. Serious Adverse Event (SAE) reporting after the End of Study visit is described in [Section 9.2.2](#) (SAE reporting).

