6.2 Treatment arms

Study treatments are defined as:

- A: indacaterol maleate 150 μ g via Concept1 device
- B: indacaterol acetate 150 μ g via Concept1 device
- C: matching placebo capsules to indacaterol via Concept1 device

Subjects will be randomized to one of the following six treatment sequences (defined according to a Williams design for 3 treatments and 3 periods) in the ratio of 1:1:1:1:1:1.

Table 6-2 Definition of treatment sequences

Sequence	Period 1	Period 2	Period 3
1	A	B	C
2	B	C	A
3	C	A	B
4	A	C	B
5	B	A	C
6	C	B	A

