11.5.2 Safety

Vital signs

All vital signs data will be listed by treatment sequence, subject, and visit/time and if ranges are available abnormalities (and relevant orthostatic changes) will be flagged. Summary statistics will be provided by treatment and visit/time.

ECG evaluations

All ECG data will be listed by treatment sequence, subject and visit/time, abnormalities will be flagged. Summary statistics will be provided by treatment and visit/time. Summary table for percentage and number of subjects with abnormal values <40 /40-90 />90 bpm in heart rate and summary table for percentage and number of subjects with notable values increase >30 / increase >60 / >450 />480/>500 msec in QTcF interval will be provided.

Clinical laboratory evaluations

All laboratory data will be listed by treatment sequence, subject, and visit/time and if normal ranges are available abnormalities will be flagged. Summary statistics will be provided by treatment and visit/time.

Summary table for percentage and number of subjects with notable values for serum potassium (<3 /3-<3.5 />5.5 mmol/L) and plasma glucose (>10-15 />15 mmol/L) will be provided.

Adverse events

All information obtained on adverse events will be displayed by treatment and subject.

All study emergent adverse events will be summarized. Adverse events starting on or after the time of the first inhalation of study drug will be classified as a treatment emergent adverse event. Any adverse events that started during a washout period will be assigned to the treatment period just prior to that washout period. Any adverse events that started during the study before the time of the first inhalation of study drug of the first period will be classified as a prior adverse event.

The number and percentage of subjects with treatment emergent adverse event summaries will be produced, overall by system organ class and preferred term, overall by system organ class, preferred term and maximum severity, suspected drug-related adverse events by system organ class and preferred term, serious adverse events by system organ class and preferred term, and adverse events leading to permanent discontinuation of study drug by system organ class and preferred term with a breakdown by treatment. A subject with multiple adverse events within a body system and treatment period is only counted once towards the total of this body system and treatment.

Concomitant medications / Significant non-drug therapies

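### Protocol Table 8-1 footnote 17 confines post-screening hematology and blood chemistry to Period 3, contradicting the second schedule table, the per-period safety endpoint and Section 3.1

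*Protocol*

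**What the plan says.** **Hematology and blood chemistry**

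- Protocol Table 8-1 attaches footnote 17 to the post-screening mark for both panels: "This assessment is completed on Day 65 of Treatment period 3 only".
- The second table in Protocol 8.1, for repetitive assessments, has a column headed "Hematology Biochemistry". It is marked at 24h00 in the row block for visits 103, 203 and 303 (Days 15, 40 and 65), with no period restriction.
- Protocol 2.2 introduces the safety endpoints with "Safety assessments during each treatment period including", and both panels are in that list.
- Protocol 3.1, repeated in SAP 1.4, has subjects "discharged on Day 15 following the final PK and safety blood sample draw".
- Protocol 11.5.2 and SAP 7.2 plan for the laboratory data: "Summary statistics will be provided by treatment and visit/time".

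**Epoch completion.** The epoch-completion column of Table 8-1 also contains both panels. Footnotes 4 and 20 of that table and Section 3.1 have these assessments done once, at early termination or after all three periods. Footnote 7 of the second table asks for them after each treatment period.

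**Day 1 pre-dose.** Section 3.1 makes an exception: "Apart from the pre-dose spirometry and safety assessments on Day 1 which will only be done before Treatment period 1". Footnote 5 of Table 8-1 and footnote 4 of the second table state the opposite: "All Day 1, pre-dose assessments must be completed for Treatment period 2 and 3".

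**The concern.** A site cannot obey footnote 17 and also take the panels that the second table shows for Days 15 and 40. A site that follows the footnote does not deliver the Section 2.2 endpoint, and a draw missed in Period 1 or 2 cannot be recovered.

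The safety objective compares each salt with placebo over 14 days of treatment in each period. With panels in every period, each completer contributes hematology and chemistry under all three treatments. With a Period 3 panel only, each completer contributes under one.

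Section 8.6.4 places the liver enzymes and bilirubin in the chemistry panel. Read with a single epoch completion, footnote 17 therefore leaves completers with no scheduled liver chemistry between screening and Day 65, although Section 9.3 describes liver triggers to be watched for throughout the study. Unscheduled tests remain possible.

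The Day 1 and epoch-completion conflicts are smaller, but the second of these decides how much footnote 17 costs.

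**Working it through.** The plan states no figure on this point, so there is none to reproduce. The check compares the texts and then counts panels.

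**1. Can the texts be read together?** The second table footnotes a period restriction where it means one: its pharmacogenetic sample is limited to Period 1. The hematology/biochemistry column carries no such footnote. In the visible text, the 24h00 row schedules these panels and a PK sample but no separate potassium or glucose, so the safety draw before Day 15 discharge has no other scheduled candidate. The conflict is genuine.

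One limit: the columns of Table 8-1 are shifted in the text as read. Placing the footnote 17 mark at 24 h is an inference from the footnote's own reference to Day 65 and from the 24h00 row of the second table. The conflict does not depend on that position.

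**2. Inputs for the count**

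- Table 6-2 (A maleate, B acetate, C placebo): ABC, BCA, CAB, ACB, BAC, CBA, allocated equally.
- Section 11.7: 42 completers at 7 per sequence; 54 randomized at 9 per sequence.
- Period 3 column: C, A, B, B, C, A. Each treatment is last in 2 of 6 sequences.
- Footnote 22: an item listed both for Day 65 and for epoch completion is done once, so the two Day 65 marks give one panel.

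**3. Post-treatment panels**

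| Reading | Per treatment, 42 completers | Total | If all 54 finish |
|---|---|---|---|
| Footnote 17, epoch completion once | 2 × 7 = 14 | 3 × 14 = 42 | 2 × 9 = 18 per treatment, 54 in all |
| Second table, all periods | 42 | 3 × 42 = 126 | 54 per treatment, 162 in all |
| Footnote 17, but epoch completion after each period (footnote 7) | 42 | 126 | 54 per treatment, 162 in all |

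On the first reading 126 − 42 = 84 panels are not taken among completers, and no subject has scheduled panels on two treatments. Early discontinuations would add single panels through the epoch-completion column. Their number and split by treatment cannot be derived from the documents.

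**4. Precision, for illustration only.** Suppose a reader takes a difference in means from the summaries. Let ρ be the within-subject correlation and σ² the total variance.

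- Period 3 only: variance = 2σ²/14.
- All periods: variance = 2σ²(1 − ρ)/42.
- Ratio of standard errors = √(3/(1 − ρ)).

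The documents do not give ρ. Over an assumed range the ratio is 1.7 at ρ = 0, 2.4 at 0.5, 3.2 at 0.7 and 5.5 at 0.9.

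**5. What is untouched.** Serum potassium and glucose are scheduled on Days 1 and 14 of every period in the second table, and they are the only laboratory variables with planned notable-value tables. Trough FEV₁ does not use these panels.

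**The case against.** **Footnote 17 may be the intended rule.** It is the only text written specifically about when these panels are taken, and it is explicit. It fits footnotes 20 and 22, which describe a single end-of-study set. Against it stand a merged row for three visits, a general endpoint list and a narrative sentence that the SAP merely repeats. A reader might infer from the number of opposing texts that footnote 17 is the mistake. The documents do not settle that. Appeal to Section 8.1 as the source for timing does not help, because both tables are in it. This objection stands as to direction; the conflict remains.

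**No planned test is lost.** This is correct. Sections 11.5.2 and SAP 7.2 plan listings, flags and descriptive summaries, with no laboratory model. What is lost is the possibility of describing the same subjects under each treatment, and the stated per-period endpoint.

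**The class effects are covered.** This is also correct: Section 3.7 names potassium decrease and glucose increase, and both are measured in every period.

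**The other two conflicts are minor.** This stands too. Section 3.1 itself sends the reader to the schedule for Periods 2 and 3, and the primary model has no baseline term. A site that followed the Section 3.1 exception would lose Day 1 pre-dose FEV₁, potassium and glucose in Periods 2 and 3, and with them a spirometric record of return after washout, but no planned efficacy analysis would change. On epoch completion, footnotes 4 and 20 and Section 3.1 agree against footnote 7.

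**Conclusion.** The plan is internally inconsistent on when hematology and blood chemistry are taken, and it should be corrected. The size is 14 instead of 42 completers per treatment with a post-treatment panel. This assumes that footnote 17 is followed, that epoch completion is done once, and that completers are spread evenly over the six sequences. If footnote 7 is followed, the loss largely disappears.

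Three stronger conclusions are tempting but not supported:

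- *Treatment would be confounded with period.* It would not be. Each treatment is last in 2 of 6 randomized sequences, so the Period 3 comparison is a smaller randomized between-subject comparison.
- *At most 54 − 42 = 12 discontinuation panels could be added.* No such cap follows: 54 is approximate, 42 is an intention, and withdrawn subjects may be replaced (Sections 4, 6.3 and 7.2).
- *A 24 h urinalysis is assured in every period.* Its mark carries no footnote 17, but its timing rests on the shifted columns of Table 8-1 and the second table does not list it.

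The primary analysis, its power and its significance level are unaffected.

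**What to change.** The sponsor should state which schedule is intended and make the texts agree, in one of two ways:

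1. **Panels in every period.** Delete footnote 17. No extra visit is needed, because a PK draw is already scheduled at 24h00 in each period. The sponsor should confirm that the maximum of about 250 mL in Section 3.7.1 covers the Period 1 and 2 panels; the public text gives no volume per panel and refers to a blood log that is not in these documents.
2. **Day 65 only.** Remove the 24h00 mark for visits 103 and 203, amend the endpoint in Section 2.2 and the Day 15 sentence in Section 3.1 and SAP 1.4, and label the hematology and chemistry summaries in Section 11.5.2 and SAP 7.2 as Period 3 only.

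Settle epoch completion at the same time, by reconciling footnote 7 of the second table with footnotes 4 and 20 of Table 8-1 and with Section 3.1. As a further minor edit, reconcile the Day 1 exception in Section 3.1 with footnote 5 of Table 8-1, footnote 4 of the second table and the rows for visits 101, 201 and 301.

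The cost is a written protocol amendment with the approvals in Section 13.1. The first option is a short edit with no SAP change; the second touches more places and both documents. Neither changes the design or the analysis model.
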